The objective of this study is to evaluate the safety, efficacy and efficiency of rapid anticoagulation reversal with protamine sulfate vs routine ACT monitoring in patients undergoing catheter based ablation of atrial fibrillation. We hypothesize that the routine use of protamine sulfate will facilitate early sheath removal, early ambulation, and improve patient comfort with a significant decrease in the rate of vascular access site complications and time to ambulation. The primary study endpoint will be the 30-day occurrence of vascular access site complications (major or minor groin bleeding including hematoma formation, aneurysm, pseudoaneurysm, AV fistula, deep venous thrombosis).

Methods and Study Protocol:

Study design:

Single center, controlled, prospective, superiority, parallel-group, open-label, randomized clinical trial.

Study Site:

Electrophysiology laboratories and outpatient clinics at the University of Michigan Health System Frankel Cardiovascular Center.

Study Population and Enrollment:

Adult patients undergoing clinically indicated RFA or cryoballoon ablation for atrial fibrillation or atrial flutter (left atrial) will be prospectively enrolled. Consideration for enrollment and obtainment of patient consent will be performed in the pre-operative setting in the cardiac procedures unit prior to the ablation procedure. Consent will be obtained by the study coordinator using both verbal and written study information.

Inclusion Criteria:

- Patient's referred for RFA or cryoablation for atrial fibrillation or atrial flutter (left atrial).
- Age ≥ 18 year
- Patients who are mentally and linguistically able to understand the aim of the trial, comply with the trial protocol, verbally acknowledge the risks, benefits, and alternatives in this trial.

Exclusion Criteria:

- Previous intolerance or allergy to heparin products.
- Current or prior administration of protamine products
-
- History of femoral access site complications including hematoma, AV fistula, pseudoaneurysm, aneurysm.
- Known lower extremity venous thrombosis.
- Coagulopathy or blood dyscrasias.
- Active malignancy.
- Thrombocytosis (platelet count $>600k/\mu l$) or thrombocytopenia (platelet count $<100k/\mu l$)
- Planned use of vascular closure device

Randomization:

A randomization will be performed in a block manner. Patients will be randomized to one of two parallel treatment strategies, namely protamine sulfate group or standard sheath removal group (control).

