Pre-Procedural and Procedural Management:

A pre-procedure groin and lower extremity examination will be documented. Patients on warfarin will continue on uninterrupted therapeutic anticoagulation through the procedure. Patients on direct-acting oral anticoagulants will discontinue the medication one dose prior to their procedure and will resume taking it after hemostasis has been achieved post-procedurally. Prior to heparin administration, ACT will be checked as a target for anticoagulation reversal prior to sheath removal.

Patients will undergo routine pre-procedural assessment and selection of radio frequency ablation (RFA) or cryoablation at the discretion of the treating physician. Procedural endpoints and ablation targets (i.e. pulmonary vein isolation, targeting of complex atrial fractionated electrograms, linear ablation lines, et cetera) are not specified by this protocol and will be performed at the discretion of the treating physician and in accordance with the ablation method selected. An intraprocedural targeted ACT of 300-400s is recommended in accordance with the current guidelines.

Vascular access will be obtained using fluoroscopic and ultrasound guidance using the standard modified-Seldinger technique. Patients undergoing RFA will have right femoral vein access with the use of two 8.5F long-sheaths and one 8F short-sheath. Patients undergoing cryoballoon ablation will have right or both femoral vein access with the use of a 14F long-sheath and 8F short sheath.

Postprocedural management:

Patients randomized to the intervention group will receive a test dose of protamine sulfate 0.5 mg with close monitoring for adverse reactions. If no reactions occur after 5 minutes patients will continue with the intervention group or otherwise undergo routine sheath removal. Protamine sulfate dose will be determined by the amount of heparin received during the last hour of the procedure (1mg of protamine per 100 units of heparin, maximum of 50 mg) and will be administered over 5 minutes, with close hemodynamic monitoring during and after the infusion. ACT levels will then be monitored with a goal ACT of <200s or return to preprocedural baseline.

The non-intervention group will undergo routine ACT measurements beginning 90min after the cessation of the procedure with a goal ACT<200s or return to preprocedural baseline before sheath removal.

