Manual compression using the standard technique by professional staff, will be applied until hemostasis is achieved, followed by a 6-hour period of flat time before ambulation. Patients will be monitored overnight for post-procedural observation which is the current standard of care in our laboratory.

Immediately after the sheath removal and the morning after the procedure, detailed examination of both groins will be performed for signs of bleeding, hematoma, aneurysm, or fistula as standard of care and will be carefully documented. Patients with signs or symptoms of vascular complications will undergo duplex venous ultrasound as usual standard of care. In addition Hemoglobin and hematocrit levels will be documented before and the morning after the procedure as per routine clinical care protocol.

Post-procedural anticoagulation will be administered for at least two months per national guideline recommendations; choice of anticoagulation and duration beyond two months will be at the discretion of the treating physician.

Data Collection and Analysis:

Baseline demographic, clinical, procedural and ultrasound data will be collected. Patients will be monitored overnight post procedure (18-24 hours) with routine assessment of clinical access site, neurologic checks, and patient comfort scores. Patients will have one-week phone follow up and three month clinical visits to assess thromboembolic and bleeding events as well as procedural outcomes. Data collection formed is shown (see attached form).

Vascular ultrasound will be obtained if clinically indicated as described above. Results will be interpreted by two independent, qualified readers to ensure standardization and accuracy. Discrepant interpretations will be jointly reviewed for agreement.

Study endpoints:

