The primary study outcome will be total time to ambulation; the start time (time zero) will be procedural termination. Secondary endpoints will include the 90-day occurrence of vascular access site complications defined as hematoma formation, aneurysm, pseudoaneurysm, arteriovenous fistula formation, access-site related major bleeding (defined as BARC type 3a or 5[18]), or procedural intervention for access complications (surgical repair, thrombin injection, et cetera). Additional exploratory endpoints will be the time to achieve hemostasis, duration of manual compression, need for repeat manual compressions, the total number of re-bleeding events, patient reported hematoma on 7 day phone call, and patient reported groin pain at discharge, 7 day phone call, and follow up appointment.

Safety endpoints:

Safety endpoints will be thrombotic events defined as stroke or transient ischemic attack, deep vein thrombosis, pulmonary embolism, lower extremity thromboembolic events, acute myocardial infarction, or death. There is no plan for an interim analysis.

Statistical Analysis:

Based on preexisting studies and an audit of quality data from our own laboratory, we anticipate a baseline time-to-ambulation of 360 ± 180 min with a reduction to 270 min with the use of protamine. We estimate that the enrollment of 150 patients would provide 80% power to detect the anticipated difference in the primary outcome at the 5% two-sided level of significance, assuming a 10% loss to follow up. Prespecified sub-groups for secondary analysis include sex, age, clinical comorbidites (BMI, diabetes, CHF), ablation method, use of antiplatelet medications, prior ablation procedure, prior coronary angiography or intervention.

Data will be reported as means and standard deviations or as absolute values and percentages where appropriate. The Chi Square and Fisher's exact test will be used to compare categorical

variables. Unpaired or paired Student's t-test or the Mann-Whitney test will be used as appropriate. A P value less than 0.05 will be considered statistically significant.

Clinical Significance:

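### Ablation method, chosen before the procedure, is left out of the primary comparison of time to ambulation; adjusting for it is a cheap improvement with an uncertain gain in precision

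*Combined protocol and SAP*

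**What the plan says.** Under Study endpoints: "The primary study outcome will be total time to ambulation", counted from the end of the procedure. Statistical Analysis sizes the trial on means of 360 and 270 minutes with SD 180, and says data will be summarised as means and SDs. For continuous variables it allows a paired or unpaired "t-test or the Mann-Whitney test will be used as appropriate". No adjusted model, effect estimate or confidence interval is named.

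Ablation method appears in the analysis once, in the subgroup list: "Prespecified sub-groups for secondary analysis include sex, age, clinical comorbidites (BMI, diabetes, CHF), ablation method".

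Pre-Procedural and Procedural Management places the choice of method before the procedure ("routine pre-procedural assessment and selection of radio frequency ablation (RFA) or cryoablation") and ties the sheaths to it:

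- RFA: "Patients undergoing RFA will have right femoral vein access with the use of two 8.5F long-sheaths and one 8F short-sheath"
- Cryoballoon: "Patients undergoing cryoballoon ablation will have right or both femoral vein access with the use of a 14F long-sheath and 8F short sheath"

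On allocation, the Randomization section says "A randomization will be performed in a block manner". It names no stratification factor and does not say when assignment happens relative to the choice of method.

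**The concern.** Ablation method is settled before protamine can act, and it decides the number and calibre of the venous sheaths, so it could plausibly affect how long haemostasis and ambulation take. The sponsor thought it important enough to list as a subgroup factor. Since no stratification is stated, the arms may differ in their RFA/cryo mix by chance.

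A covariate of this kind in the primary model can narrow the interval for the minutes saved and remove the shift that a chance imbalance would cause. The plan passes this up, although it costs almost nothing. What is at stake is some precision on the main estimate, not the validity of the trial.

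**Working it through.** **Inputs.** From Statistical Analysis: difference 360 − 270 = 90 min, SD 180, two-sided 5%, 150 enrolled, 10% loss, so 150 × 0.9 = 135 evaluable. Assumed because not stated: 1:1 allocation (67 v 68), equal SD in both arms, half of patients on cryo (20% as an alternative), and the share of outcome variance explained by method (R2).

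**The plan's own figure.** Normal formula: n per arm = 2 × (1.96 + 0.84)² × (180/90)² ≈ 63, total 126, and 126/0.9 = 140. The t-test version gives 64 per arm, 128/0.9 → 143. Allowing for the Mann-Whitney relative efficiency of 0.955 gives 147 to 152, depending on formula and rounding. The plan does not say which it used, but 150 is adequate by all of them bar the top of that last range. At 135 evaluable, exact t-test power is 82.2%, the 95% CI half-width is about 61 min, and Mann-Whitney power is 80.4%.

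**What a given R2 requires.** For a two-level factor with cryo share p, gap = SD × √R2 / √(p(1−p)). With SD 180 and p = 0.5, R2 of 5%, 10% and 20% needs RFA–cryo gaps of 80, 114 and 161 min.

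**Adjusted analysis.** Simulated regression on arm and method with robust (HC2) standard errors, 67 v 68, within-arm SD 180, half cryo. The unadjusted analysis gives about 82% and 61.2 min throughout.

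| R2 (gap) | Same gap in both arms: power, half-width | Gap in control arm only: power, half-width |
|---|---|---|
| 0 | 82%, 61.4 min | – |
| 5% (80 min) | 84%, 59.9 min | 82%, 61.0 min |
| 10% (114 min) | 85–86%, 58.2 min | 83%, 60.6 min |
| 20% (161 min) | 89–90%, 54.9 min | 84%, 59.9 min |

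The R2 labels apply to the same-gap column; the control-only column uses the same gaps. Type I error of the adjusted test was 0.048 at R2 0 and 0.051 at R2 10%. With 20% on cryo and the same gap in both arms, the results are within about half a point.

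**Cost if method is irrelevant.** About 0.3 power points and 0.2 min of half-width. Break-even is at R2 ≈ 1/131 = 0.76%, a gap of 31 min (half cryo) or 39 min (20% cryo).

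**Chance imbalance.** The exact binomial probability that the arms differ by more than 10 percentage points in method is 23% (half cryo) or 16% (20% cryo). The unadjusted standard error already allows for this.

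**Smaller SD.** The audit under Frankel Cardiovascular Center Experience gives 204 ± 47 min to sheath removal. If 47 were the SD of time to ambulation (an assumption), power would be about 100% either way. The half-width would go from 15.97 min to 15.62, 15.21 and 14.34 at R2 of 5%, 10% and 20%, a narrowing of about 0.4 to 1.6 min.

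**Skewness.** With lognormal times, the same means and SD 180 in both arms, Mann-Whitney has 96% power against 82% for the mean difference. With normal times the order reverses slightly (about 80% v 82%).

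**The case against.** The strongest objection is that adjustment is a preference. No section links ablation method to ambulation time, every R2 above is assumed, and the gaps needed for a visible gain are large. With SD 47 and half on cryo, the gap could not exceed 47/0.5 = 94 min even if method explained everything. The route also matters: if method acts through how slowly the ACT falls, protamine should largely remove that effect in its own arm, and most of the gain goes with it, as the control-only column shows. Other variables, such as pre-heparin ACT, BMI or antiplatelet use, could be argued for on similar grounds. The Randomization section is silent on strata, which does not exclude them, and the data form is not available to show whether planned method is captured before assignment.

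Most of this stands, and it limits the size of the claim. It does not remove the case for the change. Method is fixed in advance, already of interest to the sponsor, tied by the protocol to the sheaths, and nearly free to include.

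Three stronger readings are tempting and should be resisted:

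- **That the unadjusted test is wrong or the trial underpowered.** It is valid, and 150 patients suffice on the plan's inputs.
- **That the open choice of test inflates type I error.** Taking whichever of t-test and Mann-Whitney is significant gave about 6.2% (normal) to 7.0% (lognormal) in simulation. But nothing in the plan says the choice would be made that way, and sizing and reporting in means already point to a comparison of means. Naming one test is missing detail and does not carry this point.
- **That power of 89–90% is the expected gain.** It needs a 161 min gap, equal in both arms, which no section supports.

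**Conclusion.** The point holds as a low-severity improvement to consider. On the plan's inputs, with half on cryo assumed, adjusting for planned method moves power from 82% to somewhere in 82–90% for R2 of 0–20% if the effect is the same in both arms, and to about 82–84% at the same gaps if it acts in the control arm only. With an SD near 47 min, only a minute or so of interval width is gained. A modest gain, possibly none, is the reasonable expectation.

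These figures rest on planning inputs that have their own difficulties. Objective and Hypothesis names access-site complications within 30 days as the primary endpoint, whereas Study endpoints names time to ambulation. Means of 360 and 270 min from the end of the procedure do not fit Postprocedural management, where compression to haemostasis is "followed by a 6-hour period of flat time before ambulation". Both are separate matters, and the passages must be reconciled.

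**What to change.** In Statistical Analysis, state for time to ambulation:

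- Primary analysis: linear regression of minutes on randomised arm and planned ablation method (RFA or cryo, as recorded before the arm is known), all patients analysed as randomised, with robust standard errors. Report the adjusted mean difference with 95% CI.
- Show the unadjusted mean difference with 95% CI alongside.
- Sensitivity analysis: Mann-Whitney. A model that adds pre-heparin ACT is optional.
- If planned method cannot be recorded before assignment, make the unadjusted mean difference with 95% CI primary.

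The cost is a few sentences, plus a check that the data form captures planned method before assignment. Sample size and conduct are unchanged. There are two downsides to accept knowingly: about 0.3 power points lost if method explains nothing, and, as with any mean-based primary analysis, less power than Mann-Whitney if times prove strongly right-skewed.

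### One unrestricted P<0.05 rule covers every comparison; once the primary endpoint is reconciled, a short test order with all else reported as estimates would bound the error at little cost.

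*Combined protocol and SAP*

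**What the plan says.** All references are to the combined protocol and SAP.

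- **Decision rule (Statistical Analysis).** After assigning tests by type of variable, the section closes with "A P value less than 0.05 will be considered statistically significant". The rule is not confined to any endpoint.
- **Endpoints (Study endpoints; Safety endpoints).** Time to ambulation is primary. One secondary endpoint is named, a 90-day access-site complication composite, in a list worded so that others could be added. The exploratory list begins "Additional exploratory endpoints will be the time to achieve hemostasis, duration of manual compression, need for repeat manual compressions" and continues with re-bleeding, patient-reported hematoma at day 7 and groin pain at three time points. Thrombotic events form the safety endpoint. No interim analysis is planned.
- **Subgroups (Statistical Analysis).** Nine factors are prespecified for secondary analysis.
- **Hypothesis (Objective and Hypothesis).** Protamine is expected to bring benefit "with a significant decrease in the rate of vascular access site complications and time to ambulation". The same section names 30-day access-site complications, including deep venous thrombosis, as the primary endpoint. The Study endpoints section does not.
- **Where the 5% level is tied to one endpoint.** The sample-size sentence refers to the "primary outcome at the 5% two-sided level of significance, assuming a 10% loss to follow up".

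The document contains no test order, alpha split, multiplicity adjustment or statement that any P value is descriptive.

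**The concern.** Read literally, the rule lets any listed comparison be called statistically significant on its own P value, whatever happens to the primary outcome. Two things are at stake.

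First, an isolated small P value on one of many groin outcomes could be presented as a finding. The trial is open-label, and several of these outcomes are patient-reported or depend on staff judgement, so isolated positives call for particular caution.

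Second, the complication claim is central to the trial's rationale: it appears in the hypothesis and again under Clinical Significance. Yet no rule links it to the primary test, so the error rate for the two claims taken together is not controlled at 5%.

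**Working it through.** **1. The plan's own figure.** The document states no familywise error rate. Its one quantitative anchor is the sample size: "we anticipate a baseline time-to-ambulation of 360 ± 180 min with a reduction to 270 min with the use of protamine", two-sided 5%, 80% power, 10% loss, 150 patients. It says "Patients will be randomized to one of two parallel treatment strategies" without giving a ratio, so 1:1 is assumed.

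- Normal approximation: n per arm = 2 × (1.96 + 0.84)² × (180/90)² ≈ 63. Total 126, and 126/0.9 = 140.
- t-test: 64 per arm. Total 128, and 128/0.9 gives 143.
- Mann-Whitney (dividing by the relative efficiency 3/π ≈ 0.955): 66 to 68 per arm, or 147 to 152 after loss.

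So 150 agrees with the Mann-Whitney calculation and is slightly generous for a t-test. After 10% loss, 150 × 0.9 = 135, about 67 per arm. Power is then 81.9% (t-test) or 80.1% (Mann-Whitney).

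**2. Count of comparisons.** Complication composite 1 + thrombotic safety composite 1 + exploratory 8 = 10 non-primary comparisons. The eight exploratory ones are time to hemostasis, compression duration, repeat compression, re-bleeding, day-7 hematoma and groin pain three times.

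**3. Chance of at least one P<0.05 when no true effect exists.** For k independent tests it is 1 − 0.95^k. For correlated tests, equicorrelated normal statistics were simulated (200,000 runs). The correlations are assumptions, because the documents give none.

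| Comparisons, each at 5% | Independent | Correlation 0.5 | Correlation 0.7 |
|---|---|---|---|
| 8 exploratory | 34% | 25% | 19% |
| 10 non-primary | 40% | 29% | 21% |

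At correlation 0.3 the ten-test figure is 35%. Counting only false results in the direction of benefit, ten independent tests give 1 − 0.975^10 = 22.4%.

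**4. Allowance for discrete tests.** With 67 per arm, the true size of Fisher's exact test at nominal 5% is 1.8% at a 6.9% event rate (the Medicare figure in the Background), 2.4% at 10%, and effectively zero at 0.5% (the centre's stated ceiling for embolic events). If five of the ten tests ran at an assumed true level of 2.5%, the independent figure would be 1 − 0.95^5 × 0.975^5 = 32%, with 23% and 17% at correlations of 0.5 and 0.7.

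**5. Primary and complication composite as a pair.** Each at 5%, independent, both null: 1 − 0.95² = 9.75%. In a fixed order the pair is held at 5%. If the primary has no effect, a false claim on either endpoint requires a false rejection of the primary first. If the primary has an effect, only the second test can err.

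**6. What the order costs the composite.** If the two tests are independent, the chance of claiming the composite is 0.80 × its own power. The illustrative rates are percentages reported in the Background and Table 1, with Fisher's exact test at 67 per arm:

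- 6.3% vs 1.1%: own power 14%, and 0.80 × 14% = 11%.
- 11% vs 0%: own power 76%, and 0.80 × 76% = 61%. The counts printed beside these percentages in Table 1 do not match them, so only the percentages are used.

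**7. Subgroups.** Adding the primary and nine subgroup factors, each counted once, makes 20 tests: 1 − 0.95^20 = 64% if independent.

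**The case against.** The plan already ranks its endpoints as primary, secondary, exploratory and safety. It ties the two-sided 5% level and the sample size to the primary, since "enrollment of 150 patients would provide 80% power to detect the anticipated difference in the primary outcome", and it has no interim look. On this view the quoted sentence is a conventional threshold, and a reader would discount anything labelled exploratory. This has some force: the plan does not say that an exploratory P<0.05 will be reported as a benefit or a harm, and that should not be imputed to it. But the labels do not alter the decision rule, and the sample-size sentence limits no claim elsewhere.

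A reader might also infer that a false significant secondary result is likely. The documents do not support that. Only one secondary endpoint is named, and its own false-positive risk is at most about 5%, or about 1.8% with Fisher's exact test at a 6.9% event rate. The larger figures come mainly from the exploratory endpoints. Across all ten comparisons the risk stays below one half, and it assumes no effect on any of them. If protamine truly affects some, fewer false positives are possible. The independent-test figure passes 50% here only when the subgroup tests are added.

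Finally, no order can be fixed while two sections name different primary endpoints. That stands, and it comes first in the remedy.

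**Conclusion.** The concern holds as a material but moderate gap. One unrestricted threshold covers everything, and nothing limits non-primary claims. The risk of at least one false significant result among the ten non-primary comparisons is at most about 40% if independent and 21% to 29% at correlations of 0.7 to 0.5, with lower values where exact tests are conservative. The pair that carries the trial's main claims has up to 9.75% familywise error.

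These figures rest on no true effect for the endpoints counted, on assumed correlations and on 1:1 allocation. The safety endpoint is counted as one composite.

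A reader might also conclude that a fixed test order is free. That is true only for the primary: the complication composite loses its claim whenever the primary fails. The defect does not undermine the primary analysis. It is worth correcting because the repair is cheap.

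**What to change.** 1. Reconcile the Objective and Hypothesis section (30-day complications as primary) with the Study endpoints section (time to ambulation as primary), including the 30- versus 90-day window and whether deep vein thrombosis belongs to the complication composite or to safety.
2. Then replace the general significance sentence with:

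> The primary outcome is tested at two-sided 5%. Only if it is significant is the key secondary tested at two-sided 5%. All exploratory, safety and subgroup results are reported as estimates with 95% CIs and are not called statistically significant.

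Under the Study endpoints section, the key secondary is the 90-day complication composite. Safety signals remain fully visible through their estimates and intervals.

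**Cost.** A few sentences. With time to ambulation as primary, the sample size of 150, primary alpha and primary power are unchanged. The key secondary is tested at the full 5% only after the primary succeeds, so its chance of being claimed is about 0.80 times its own power if independent. Nothing is placed behind it, so no later endpoint is blocked. Exploratory, safety and subgroup results lose the significance label. If complications were kept as primary instead, the stated 80% power would not carry over, because the sample size was calculated for time to ambulation.
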